- If this change necessitates modifications to the ICD or addendum ICD, please indicate below and include the requested modifications at this time.

Investigator's Brochure/Product Information (ex. package insert, device manual, etc.) **version and date:**
Do the changes to the IB or Product Information require modifications to the approved ICD? No Yes
If yes, please indicate below and include the requested modifications at this time.
If no, please attach a rationale for modifications not being necessary.

- Include a detailed summary of changes
- Include copy of revised Investigator's Brochure/Product Information

Informed consent document (ICD) revisions

- Include a copy of the most current IRB-approved ICD indicating changes (tracked changes [contact our office for the Microsoft Word version] or handwritten changes are acceptable for minor revisions)

New additional informed consent document/addendum
Please note: Please remove all formatting such as shading, text boxes, comments or hidden text from the ICDs before submitting to Salus IRB. ICDs submitted with such formatting may cause a delay in the review of this request and may result in additional administrative fees.

SPONSOR: GUARDiON HEALTH SCIENCES

PROTOCOL #: 1

Recruitment and Study Material

Please forward the Microsoft Word version of each file requiring review. Include the document title and version (number or date) in each file.

New material Revised material

Identify which items and the quantity being submitted.

 Proposed printed advertisement, #	 Proposed web site content, #
 Script of proposed video recording, #	 Script of proposed audio recording, #
 Participant screening tool, #	 Participant Diaries, #
 Survey instrument(s), #	 Questionnaire(s), #
 Participant education material, #	
 Other (describe): #	

Request for Salus IRB to Translate Study Documents:

- What documents would you like translated?
 - Consent Forms
 - Recruitment Material
 - Study Materials
- What language would you like them translated into? Language:
- Do you require a quote before proceeding with the translation? Yes No
- Do you require back-translation? Yes No

Translated Documents:

- Please ensure the following is attached to this request:

27 DEC 2017

Controlled Study of the Effect of a Medical Food
Containing All Three Macular Carotenoids and Essential Cofactors
Compared to AREDS2 on Early Macular Degeneration

PURPOSE:

This 6-month randomized control study is undertaken to compare the effect of treatment with LumegaZ, a medical food containing lutein, zeaxanthin, and meso-zeaxanthin, as well as essential cofactors, other antioxidants, and mitochondrial support, with the effect of treatment with AREDS2. Patients with early macular degeneration, defined as photographically visible drusen with or without abnormal dark adaptation on the AdaptDx will be randomized 2:1 and both groups will be compared to untreated patients with normal dark adaptation.

BACKGROUND:

Macular degeneration is the most common cause of blindness in people over the age of 60. The incidence of macular degeneration at all stages is 1 in 8 and is more common than diabetes and glaucoma at the same age.

The dietary carotenoids lutein and zeaxanthin (derived primarily from leafy green vegetables and other colored fruits and vegetables) as well as meso-zeaxanthin, a metabolite of lutein, are stored in the macula in all healthy retinas. This area serves central vision, and is the specific area that is affected by macular degeneration. The accumulation of these pigments results in a yellowish coloration of the retina, the concentration of which is called macular pigment density. A large multicenter trial called AREDS 2 (2013) showed that supplementing lutein and zeaxanthin reduced progression of moderate to advanced AMD by 25%. The CREST (2014) and MOST (2015) studies showed that supplementation of all 3 macular pigments resulted in normalization of the macular pigment profile and improvement in contrast sensitivity in early AMD. All 3 macular carotenoids are recognized by the FDA as 'generally regarded as safe (GRAS) for supplementation in foods.

Macular degeneration can be understood as a disease of excessive oxidation of the retinal tissue with genetic, age, dietary and light exposure components leading to accumulation of oxidized cholesterol and polyunsaturated fatty acids both on Bruch's membrane and between Bruch's membrane and the retinal pigment epithelium in a condition analogous to plaque

buildup in arteries. These deposits block transfer of waste out of the retina leading to more accumulation and block transfer of nutrients into the retina. In macular degeneration, not enough Vitamin A crosses Bruch's membrane because of the build-up, causing a localized deficiency of Retinol in the parafoveal rods. This causes slower dark adaptation after bleaching light, which is the earliest symptom of macular degeneration: difficulty driving in darkness or adapting to dark conditions increasing with aging.

Abnormal dark adaptation found by AdaptDX testing is the earliest clinical sign of macular degeneration. This has enabled diagnosis of subclinical macular degeneration with 90% positive and negative test reliability, 3-5 years before the first drusen is visible clinically. Those patients who exhibit impaired dark adaptation, whether they are subclinical with no drusen or early with mild drusen, may benefit from nutritional and /or lifestyle changes which could significantly slow the progression of the disease. This would result in maintenance of retinal health and visual performance.

It is clear that early, effective intervention in any disease process is the key to reducing morbidity. Earlier diagnosis of macular degeneration is now possible with AdaptDX testing. Effective intervention involves reducing the photo-oxidative damage of the retina caused by the visual process in the retina, and potential clearing of the early stage blockage of bidirectional transport across Bruch's membrane. Thirty percent of people over age 60 have abnormal dark adaptation. Likewise, 30% of people have an abnormal spatial profile of macular pigment indicating insufficient meso-zeaxanthin creation from lutein. Supplementing meso-zeaxanthin as well as lutein and zeaxanthin can restore the macular pigment spatial profile and improve visual performance in early macular degeneration. Early results from an as yet unpublished exploratory study in progress with such supplementation in subclinical AMD indicate improvement in MPOD and best corrected contrast sensitivity in many patients by 6 months.

A medical food is a special category of supplement approval by the FDA where physicians prescribe it for nutritional treatment of specific medical conditions. The medical food to be used by patients in this study contains not only all the macular carotenoids in micelle formulation for improved absorption, but also significant cofactors, such as vitamins, minerals, ALA, astaxanthin, N-acetylcysteine, carnosine and others. All of these ingredients working together should significantly improve the mitochondrial, antioxidant and anti-inflammatory functions of the retina. This should allow creation of less damage to critical elements of the retina and less toxic waste such as oxidized cholesterol and oxidized polyunsaturated fatty acids which are the major components of the sub-RPE and Bruch's membrane deposits. This controlled study will attempt to show that using a medical food designed to optimize retinal metabolism and antioxidant capacity will exert a positive effect in subclinical macular degeneration, which is greater than supplementation with AREDS2 and will also improve measured functions into the range of function in untreated normal patients.

STUDY:

All study candidates are routine patients in a general ophthalmology practice. All patients who are interested will be offered the opportunity to participate in this controlled study of the effect of a nutritional food on subclinical macular degeneration. Each patient will undergo a screening AdaptDx to separate patients with normal dark adaptation from those with abnormal dark adaptation. All patients will receive the same exams at baseline, 3 months and 6 months. For details, see the listing below. Those who are confirmed as normal with extended dark adaptation testing will receive no treatment precisely because they are defined as not having a problem needing this treatment. Those who are confirmed with early macular degeneration by photographically visible drusen and have dark adaptation scores of less than 10 minutes will receive treatment by ingesting a commercially available medical food, containing all 3 macular pigment as well as essential cofactors and other antioxidants, or AREDS2, randomized 2:1 for 6 months. If positive effects are noted, it is possible that the study might be extended. The tasks below are part of standard diagnostic clinical eyecare practice.

- Baseline, 3 month and 6 month examinations
 - History
 - Risk factors
 - Best corrected visual acuity
 - Best corrected contrast sensitivity (CSV 1000)
 - Intraocular pressure, nondilated slit-lamp exam
 - Dark adaptation (AdaptDX, extended exam)
 - Macular pigment optical density (MapcatSF)
 - Macular ocular coherence tomography (Zeiss Cirrus OCT)
 - Fundus photography (Zeiss VisuCam Pro)

Because these patients will have additional problems found in routine clinical practice, other exams may occur for other problems and will not be considered part of the study data. Should any adverse effects be noted thought to be from the study treatment, the patient will be examined to understand the effect and if it is felt to be not significant, the patient will be asked to continue in the study. In the highly unlikely event a serious adverse effect is noted the patient will be terminated from the study and appropriate treatment will be undertaken.

DATA COLLECTION:

The data will be maintained on standardized forms and printable graphics, as well as in the patient's routine clinical file. To protect identifiable information, files will be locked in a file cabinet, accessible only the PI and the study coordinator. Data will be transcribed without

personally identifiable information into standard Excel files and analyzed as appropriate using standard statistical techniques.

STUDY REQUIREMENTS:

This study will be conducted with the protocol, good clinical practices and applicable regulatory requirements. This is a no significant risk study, using commercially available supplements, Lumega-Z or AREDS2, containing 2 or 3 of the three carotenoids that are FDA “generally recognized as safe” for food supplementation and are found in all healthy retinas. All examinations are noninvasive and are performed with FDA cleared, commercially available medical devices in routine clinical use.

The study population consists of 90 male and female patients in a routine clinical practice age 60 and over who have early macular degeneration as defined as a few drusen visible on Visucam and have an AdaptDx score less than or equal to 10 minutes. No vulnerable populations will be studied.

The patient will be studied for improvements in ocular function. Primary endpoints would be improvement in macular pigment optical density long form, improvement in best corrected contrast sensitivity and improvement in best corrected vision. Secondary endpoints would be improvement of AdaptDx long form time or a reduction in drusen.

The study supplements for each

study subject will be kept in a locked cabinet until dispensed by study staff not involved with testing to the subject.

A protocol deviation log and an adverse effect log will be kept for each subject. Immediate attention will be paid to any serious adverse events, which by the nature of the study are completely unexpected. If any injuries occur to subjects in the protocol , they are considered to be under treatment for early AMD, (diagnosis AMD, ICD H35.3131) and will be dealt with as any other medical condition or complication of treatment.

Data will be reviewed for safety and unexpected positive or negative effects after three and six month visit period are completed for all subjects.

Data will be collected in the subjects routine electronic medical record and confirmed as complete on a hard copy visit log in a study folder for each subject. Copies of each visit will be kept in the study folder. There will be a protocol deviation log, adverse events log and a study supplement log in each subjects folder.

The information collected will be used in anonymous group data analysis to be prepared for submission for potential publication. The information will not be sold or used in future research. The data can be verified through the audit trail in the subject's individual electronic medical record original source. No data will be stored on a portable device. The data will not be destroyed because it is part of medical record of care of AMD unspecified for an individual and is subject to the laws of the state of Texas and the rules of the state medical board.

[name] • P: [contact] • F: [contact] • [contact]

If you require assistance answering any of the questions on this form,
please contact the Salus IRB at the number listed above.

Sponsor: Guardian Health Sciences, Inc

Protocol #: LungeaZ#1

JT 31Oct 17

A. ADMINISTRATIVE INFORMATION:

How did you learn of Salus IRB?

We are an existing client of Salus IRB Sponsor/CRO recommendation Tradeshow
 Industry Publication Internet/Website
 Other:

Sponsor Contact Information:

1.	Name of sponsor contact:	[name]
2.	Sponsor name:	Guardian Health Sciences, Inc
3.	[contact]
4.	Email:	[contact]

Provide the Primary Contact Information for IRB inquiries:

5.	Primary contact:	 Sponsor  CRO  Other: PI
6.	Name of primary contact:	[name]
7.	Name of company:	Eye Clinic of Austin

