At the end of the trial period, data will be collected by the Principal Investigator and analyzed by professional optical engineers at Western University of Health Sciences, Pomona CA. The data provided will only contain patient ID, age, and sex, without containing any identifying details about each participant. Data will be analyzed upon measurement quality, according to the respective manufacturer procedures, in each outcome measure. In the event which data is missing or incomplete, we will evaluate the appropriate measures to include the available information and consult with qualified professionals.

Preliminary and sub-analyses will be performed using the statistical programming software, SPSS Systems. The objective is to examine the distribution and potential relationships within data sets through standardized descriptive-numerical summaries. Statistical analysis strategies may include a mixed-design Analysis Of Variance (ANOVA) to examine the following outcome measures across the three time-points of data collection; including visual acuity, contrast sensitivity, dark adaptation recovery, and MPOD levels. A post hoc sub-analysis of paired sample t-test may be used (either Bonferroni correction or Tukey test) to evaluate the change in each outcome measure parameter, if needed, in respect to each treatment group. Additionally, each group-measurement may be separated and analyzed by eye; to evaluate inter-eye differences from each treatment. Results of the statistical analysis will be analyzed as group averages of each outcome measurement.

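### The protocol does not say that adverse events are logged whatever their suspected cause or wherever they are found, and it plans no summary by arm, so harms may be under-recorded.

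*Combined protocol and SAP*

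**What the plan says.** In the STUDY section of the protocol, just after the list of study examinations, the text expects patients to have unrelated problems and rules that "other exams may occur for other problems and will not be considered part of the study data". It makes no exception for adverse events. The next sentence reads: "Should any adverse effects be noted thought to be from the study treatment, the patient will be examined to understand the effect". Serious effects are treated differently, with no causality condition: "In the highly unlikely event a serious adverse effect is noted the patient will be terminated from the study".

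STUDY REQUIREMENTS adds: "A protocol deviation log and an adverse effect log will be kept for each subject". Further on, the same section calls this an adverse events log. It also states: "Immediate attention will be paid to any serious adverse events". It promises a look at the data for safety and for unanticipated effects, good or bad, once all subjects have finished the 3-month and then the 6-month visits.

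Study exams take place at baseline, 3 months and 6 months, are the same for all patients, and include a history. The unheaded statistical analysis text at the end of the document names visual acuity, contrast sensitivity, dark adaptation and MPOD as outcome measures, and no adverse-event summary. The IRB submission form names the principal investigator as the safety monitor.

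**The concern.** An unexpected harm is usually not blamed on the product when it first appears. It shows up as an excess in one arm over another, and that excess is visible only if events are recorded without regard to suspected cause and then counted by arm. This plan states neither step.

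The setting adds to the risk. Candidates are routine patients of one ophthalmology practice, so visits outside the study schedule are likely, and these are the visits that the STUDY section sets aside. The text states no masking of patients; it only separates the staff who dispense from those who test. Willingness to attribute an event to the product could therefore differ between arms. In the untreated group there is no study treatment to blame, so the condition for examining a non-serious effect cannot be met there at all. At stake is whether a short or empty log could fairly be read as evidence of safety.

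**Working it through.** The documents give no adverse-event rate, power statement or safety figure, so there is nothing to reproduce. The check sets the rules side by side.

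**Step 1. What happens to each kind of event**

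| Event | Action stated | Is entry in the log required? |
|---|---|---|
| Serious, any cause | Yes, in STUDY and in STUDY REQUIREMENTS | Log exists; entry rule not stated |
| Non-serious, attributed to treatment | Patient is examined (STUDY) | Log exists; entry rule not stated |
| Non-serious, not attributed, found at a 3- or 6-month visit | None stated | Not stated |
| Non-serious, not attributed, found at another exam | None stated; the exam is outside the study data | Not stated |

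The log has no stated limit to attributed events, and no stated duty to include unattributed ones. The last row is the weakest. An explicit rule takes the exam out of the study data, and no rule brings an event found there back in.

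**Step 2. What would elicit an event.** The history taken at each visit is the only listed item likely to do so. There is no standard question, no definition of adverse effect or adverse event, no collection window, and no separate recording of seriousness and suspected relation.

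**Step 3. What is analysed.** Four efficacy measures are named. The promised safety review has no specified table, denominator or comparison by arm.

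**Step 4. Scale, under assumptions.** STUDY REQUIREMENTS gives 90 patients with early macular degeneration, and allocation is 2:1. Assume that all 90 are randomised, 60 to Lumega-Z and 30 to AREDS2.

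With no events in a complete log, the one-sided 95% upper limit for the true rate is 1 − 0.05^(1/n):
- n = 60: 1 − 0.05^(1/60) = 4.9%
- n = 30: 1 − 0.05^(1/30) = 9.5%

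Power for a comparison between arms (two-sided 5%, normal approximation with pooled variance under the null) is Φ[(Δ − 1.96·SE₀)/SE₁]. Take an assumed 10% on AREDS2 and 20% on Lumega-Z:
- pooled rate = (3 + 12)/90 = 0.167
- SE₀ = √(0.167 × 0.833 × (1/30 + 1/60)) = 0.083
- SE₁ = √(0.09/30 + 0.16/60) = 0.075
- (0.10 − 0.163)/0.075 = −0.84, so power is about 20%

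The same formula gives about 57% for 10% versus 30%, and 88% for 10% versus 40%. All of these figures assume complete recording. They do not show that recording will be incomplete.

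**The case against.** The strongest reply is that the plan limits an examination and an exam record, but does not limit the log. That is right as far as it goes, and it rules out several stronger readings that a reader might infer.

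- *That harms are acted on only if blamed on the product.* Serious events carry no causality condition in either section. The STUDY section also does not say who makes the judgement.
- *That attribution is the entry condition for the log.* The condition governs when a patient is examined. The log provision does not contain it.
- *That harms are certainly under-counted and cannot be compared.* Excluding an exam does not in terms exclude an event found at it. The log and the visit schedule apply to every subject, so logged events could be tabulated. The practice's own medical record is the study source, so some events could be retrieved later.
- *That injuries are filtered out because injured subjects are described this way:* "they are considered to be under treatment for early AMD". That sentence concerns care, not recording. It does sit badly with the untreated normals, of whom the STUDY section says "they are defined as not having a problem needing this treatment". The two passages should be reconciled, but this does not affect the counting of harms.
- *That events never reach the analysts because of this sentence:* "The data provided will only contain patient ID, age, and sex". It is about de-identification. Read literally, it would also bar the outcome data that the same text analyses.

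It can also be said that safety is not an endpoint, that the products are on the market, that the list of analyses is introduced as possible rather than exhaustive, and that at this size only large differences would be detected. The power figures bear out the last point.

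What the reply does not supply is the missing rule. Nothing requires unattributed events, or events from excluded exams, to be logged, and no tabulation is specified. Low power is a reason to present the counts with care. It is not a reason to leave their capture to individual judgement.

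**Conclusion.** The point holds as a gap in the rules for recording and analysis. The exclusion of other exams is an affirmative rule without an exception for harms. The log has no stated entry rule, and no adverse-event summary by arm is planned. Non-serious or unattributed harms found between scheduled visits may therefore go unrecorded, and a safety review or arm comparison built on that log would be unreliable.

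The extent of any loss is unknown, because the documents give no basis for a capture rate or for a difference in capture between arms. The limits of 4.9% and 9.5% rest on the assumed 60:30 split and describe the best case. This is worth correcting because it is cheap and improves the only harm data the trial will have. It does not undermine the efficacy comparison.

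**What to change.** 1. **STUDY section:** confine the exclusion of other exams to efficacy measurements.
2. **STUDY REQUIREMENTS:** use one defined term. State that every untoward medical event from first dispensing (baseline for the untreated group) to the 6-month visit, found at any exam, is logged regardless of suspected cause. Record seriousness and suspected relation as separate items.
3. **3- and 6-month visits:** ask one standard question about new health problems, in all groups.
4. **Statistical analysis text:** add a table of patients with any event and with any serious event, by group, with confidence intervals.
5. Reconcile the injury wording in STUDY REQUIREMENTS with the STUDY section's definition of untreated normals.

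The cost is amendment wording, one question at two existing visits, extra log lines and one table. The downside is a longer log with many unrelated entries. The change should be in place before follow-up, because events not recorded at the time may not be reliably recoverable. It concerns recording and analysis only, not how adverse effects are managed.

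### Terminating a patient from the study after a serious adverse effect ends study follow-up as well as product, so later safety data on that patient would go uncollected

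*Combined protocol and SAP*

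**What the plan says.** The adverse-effects paragraph of the protocol's STUDY section has two branches. For a lesser effect, "if it is felt to be not significant, the patient will be asked to continue in the study". For a serious one, "a serious adverse effect is noted the patient will be terminated from the study and appropriate treatment will be undertaken". Both are expressed as staying in or leaving the study. Neither mentions stopping the supplement while remaining under observation.

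Other text that bears on the rule:

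- STUDY, visit schedule: "All patients will receive the same exams at baseline, 3 months and 6 months".
- STUDY, unscheduled visits: "other exams may occur for other problems and will not be considered part of the study data".
- STUDY REQUIREMENTS, injuries: they "will be dealt with as any other medical condition or complication of treatment". The same section gives every subject an adverse-effect log.
- STUDY REQUIREMENTS, safety review: "Data will be reviewed for safety and unexpected positive or negative effects after three and six month visit period are completed for all subjects".
- Investigator statement of agreement, item 7: the investigator reports unanticipated problems promptly and sees that affected participants receive adequate care.
- Statistical analysis text: a mixed-design ANOVA over three time points is offered as a possibility. Missing data are left to later judgement, with the aim of using what is available. No analysis population is defined.

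**The concern.** Stopping a product and leaving a study are different decisions, and the rule merges them. A site following it as written has no instruction to carry out the remaining acuity, pressure, OCT and fundus examinations as study visits, or to keep recording the event until its outcome is known. The patients affected are those whose later course matters most for safety.

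The two data reviews, after the 3- and 6-month visits, are the only scheduled safety reviews in the text. The IRB application names the principal investigator as the monitor, and the box for a data safety monitoring board is not ticked. If later study data on these patients are absent, the reviews can show that a serious effect occurred but may not show, from study data, whether it resolved.

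There is also a smaller efficacy issue. Removal depends on how a patient fared on the assigned product, so any missing outcomes would not be missing at random with respect to treatment.

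**Working it through.** **1. What the text provides.** The plan states no figure on this point, so there is nothing to reproduce. The first check is of wording.

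| Question | Where answered | Answer |
|---|---|---|
| Is the event recorded? | STUDY REQUIREMENTS (log); investigator agreement, item 7 | Yes |
| Is the patient treated? | STUDY; STUDY REQUIREMENTS; item 7 | Yes |
| Are exams still due carried out as study exams? | STUDY | Schedule says all patients; the termination rule removes this patient; no text reconciles them |
| Is the event followed to its outcome as study data? | None found | Not stated |
| Are the patient's data kept in the assigned arm? | Statistical analysis text | Not stated |

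**2. How many patients.** Inputs: 90 patients and 2:1 allocation, from the protocol. Assumptions: all 90 are randomised, giving 60 and 30, and the serious-effect rate r is 1% to 5% in both arms.

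- r = 1%: 60 × 0.01 = 0.6 and 30 × 0.01 = 0.3, total 0.9.
- r = 2%: 1.2 and 0.6, total 1.8.
- r = 5%: 3.0 and 1.5, total 4.5.

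The chance that the rule is used at least once is 1 − (1 − r)^90: 60% at r = 1%, 84% at 2% and 99% at 5%.

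**3. Effect on the arm difference if these patients' outcomes are left out.** Let k1 and k2 be the shares removed from the two arms, and d the difference in outcome, in SD units, between those removed and those kept. The shift is (k1 − k2) × d.

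- 5% against 0%: d = 0.5 gives 0.05 × 0.5 = 0.025 SD; d = 1 gives 0.05 × 1 = 0.05 SD.
- 5% against 2%: d = 1 gives 0.03 × 1 = 0.03 SD.
- Equal shares and equal d: the shift is zero.

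**4. Effect on power.** The plan has no power calculation. Assume 80% power before losses at two-sided 0.05. The detectable difference is (1.960 + 0.842) × √(1/60 + 1/30) = 0.626 SD. Losing a share r from both arms gives power Φ(2.802 × √(1 − r) − 1.960).

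- r = 1%: 79.6%.
- r = 2%: 79.2%.
- r = 5%: 78.0%.

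On these assumptions the effect on efficacy is small. The loss of post-event study data does not shrink in the same way: it applies to every affected patient with an exam or an event outcome still to come.

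**The case against.** The best defence is that the rule will rarely be used and that much of what matters is captured anyway. The protocol regards a serious effect as highly unlikely with these commercially available products. The rule follows a sentence about effects attributed to the study treatment, so its trigger may be narrower than any serious event. These are patients of the practice, and the examinations are described as routine care, so later results may well reach the medical record. A specific exception also need not contradict a general visit schedule. Finally, the site form refers to the consent document for its plan on research injuries, and that document was not available for this review.

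Much of this stands, and it rules out several stronger readings that a reader might infer:

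- **That the safety review would omit these patients altogether.** It is a review of data, with no restriction to completers, and the event is logged.
- **That these patients lose both follow-up exams.** Only exams still due are lost. An event after month 3 leaves the 3-month exam intact.
- **That they necessarily leave the randomised comparison.** A standard repeated-measures ANOVA drops patients who lack a time point, but the plan only says that this method may be used and speaks of including available information.
- **That the comparison is materially biased.** Section 3 of the working does not support this at low rates.

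What remains is that routine records are not the same as planned study data. The available text does not say that examinations after termination would count, and the visit schedule and safety review are both written as covering all patients.

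**Conclusion.** The point holds as a defect in a stated rule, with modest consequences for efficacy. The protocol ends study participation after a serious adverse effect, and no available text restores the remaining exams or follow-up of the event as study data. About 1 to 5 patients would be affected if the rate is 1% to 5% and all 90 are randomised 60:30. Both are assumptions. The shift in the arm difference is about 0.025 to 0.05 SD under a one-sided 5% loss with a 0.5 to 1 SD outcome difference, and nil if losses are alike in both arms.

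The case therefore rests on safety information: how serious effects evolve, measured with the study's own examinations. Whether and when product should be stopped is a clinical matter and is not judged here. The consent document could change the conclusion if it provides for follow-up after early termination.

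**What to change.** Reconcile the adverse-effects paragraph in STUDY with the visit schedule in the same section and the safety review in STUDY REQUIREMENTS. Separate two matters that are now joined: the decision about product, which stays with the sponsor and investigator, and study follow-up. For follow-up, state that:

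- the remaining scheduled study exams are still collected, unless consent is withdrawn or the patient is unable to attend;
- the course of the event is recorded in the adverse-event log until it resolves or stabilises;
- the patient's data are kept in the assigned arm.

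The consent document should be checked so that it says the same.

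The cost is about one sentence in an amendment and continued visits for a few patients. There are two downsides. Some off-product measurements will enter the randomised comparison. These patients also keep visits for which, according to the cost statement in the IRB submission, the usual deductibles and copays apply.
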